Study Population:	Newly diagnosed breast cancer patients with an indication for post-operative radiotherapy after neo-adjuvant chemotherapy and surgery
Accrual Period:	2-3 years
Study Design:	Prospective two cohorts study in newly diagnosed breast cancer patients. Cohort 1 patients will receive Radiation to breast and chest wall. Cohort 2 patients will receive Radiation to Breast, chest wall and Level III/SCV nodes.
Study Duration:	Patients will complete treatment in three weeks (15 fractions). All patients will be followed at 3 months after the completion of treatment then yearly for the next 5 years.
Study Agent/ Intervention Description:	Cohort 1 (Post-segmental Mastectomy, post-mastectomy and Post-mastectomy with expanders or final reconstruction): Prone whole breast or chest wall 3D-CRT or IMRT at 2.7 Gy X 15 fractions (40.50 Gy) with a concomitant boost of 0.50 Gy (7.5 Gy) to the original tumor bed in post-segmental mastectomy patients or mastectomy scar in post-mastectomy patients. Patients who have undergone reconstruction will not receive concomitant boost.
	Cohort 2: In addition to receiving radiation to the original tumor bed, patients will also receive radiation to Level III axillary nodes and Supraclavicular nodes: 3D-CRT or IMRT at 2.7 Gy X 15 fraction (40.50 Gy) If clinically indicated, internal mammary nodes will also be treated and a supine set up will be used

[figure not shown]
Primary Objective: *Acute Toxicity: Grade 2-3 dermatitis <25% in each cohort*

Secondary Objective: *QOL, defined by RTOG-PRO; Late toxicity, Fibrosis, Telangiectasia, Brachial Plexopathy.*

Exploratory Objectives: *Local control; Time to Progression, Survival; Evaluation of Determinants of Breast Fibrosis*

SCHEMA

Stage I-III Breast Cancer Patients, Eligible For Post-Surgical Radiotherapy After Neo-adjuvant Chemotherapy And/Or Hormonal Therapy Followed By Segmental Mastectomy Or Mastectomy

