1.0 OBJECTIVES

1.1 Primary Objectives

- 1.1.1. To test feasibility of accelerated radiotherapy in the post-operative setting of breast cancer patients treated by neo-adjuvant chemotherapy and surgery, by evaluating the proportion of patients who experience grade II-III dermatitis within 60 days of the end of treatment.

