2.2 Experience On Accelerated Concomitant Boost Whole Breast: NYU 03-30 and 01-51

NYU 03-30. Inspired by the hypo-fractionated Canadian trial, [2] we developed a technique

that utilizes IMRT to deliver accelerated prone whole breast radiotherapy with a concomitant boost to the tumor bed. Patients with stage I or II breast cancer, excised by breast conserving surgery with negative margins, and either sentinel node biopsy or axillary dissection were eligible for this IRB-approved protocol. All patients underwent an informed consent procedure. CT simulation was performed with the patient on a dedicated prone breast board, in the exact position used for treatment. Relevant volumes contoured included the post-operative tumor bed (CTV), the ipsilateral breast volume (IBV), the heart, and the lungs. The Planning Target Volume (PTV) was defined as CTV + 1 cm. The residual breast volume (RBV) was defined as the IBV - PTV. A dose of 40.5 Gy in 15 fractions was prescribed to the IBV. An additional 0.5 Gy was delivered concomitantly to the PTV for a total dose of 48 Gy. The dose was determined by radiobiological modeling of the Biologically Effective Dose (BED), to match tumor control and risk of late effects of a standard schedule of 46 Gy to the whole breast plus a sequential boost dose of 14 Gy to the tumor bed. A value for tumor $\alpha/\beta = 4$ was used and the impact of cell proliferation during the course of treatment was taken into account. For each patient accrued to the study, blood was collected for radiation genomic studies, to explore markers predictive of late breast complications (fibrosis, retraction, and telangiectasia).

From September 2003 to August 2004, the planned accrual was completed, with 90 patients treated in the protocol (mean follow-up of 13 months, range 1-23 months). Median age was 58 (range 28-80). Median tumor size was 13 mm (range 1-40 mm). Acute toxicity was generally mild and is summarized in Table 1 using the RTOG score. Radiation dermatitis was the most common toxicity and tended to occur the week after completion of treatment.

Table 1. Acute Toxicity NYU 03-30

	Grade 1	Grade 2	Grade 3	Grade 4
Dermatitis	38 (42%)	9 (10%)	2 (2%)	-
Fatigue	15 (17%)	-	-	-
Breast edema	7 (8%)	-	-	-
Breast pain	4 (4%)	-	-	-

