Based on the experience gathered from NYU Protocol 05-181, it is rational for all patients to first undergo a CT Simulation in the prone position. In this protocol, we will again use 2.5 mm slice thickness with the patient positioned on a dedicated breast mattress that allows the index breast to freely fall through an opening. If it is found that conventional tangents in the prone position include **any** volume of heart and/or > 5% of lung volume, a second simulation will be required in supine position to assess which position best minimizes the amount of heart and lung in the treatment fields to be chosen for treatment.

2.4 NYU 09-0300: A Prospective Randomized Trial Aimed At Establishing The Optimal Boost Schedule

Radiobiological evidence supported the introduction of a larger fraction dose before a two-day treatment break (weekend). We studied two different boost schemas in a randomized trial of 400 patients. The **standard arm** was a concomitant boost protocol over three weeks which had previously been evaluated in over 500 patients (NYU 03-30 and NYU 05-16 of 60

181) and had shown excellent tolerance, and results. In addition to the 2.7 Gy whole breast dose, an additional 2 Gy was delivered to the tumor bed on each of the three Fridays, with the tumor bed receiving 4.7 Gy on each of the three Fridays.

At a median follow-up of 45 months, there were no deaths related to breast cancer. The weekly boost regimen produced no more grade ≥ 2 acute toxicity than the daily boost regimen (8.1% vs 10.4%; non-inferiority $Z = -2.52$; $p = 0.006$). There was no statistical difference in cumulative incidences of long term fibrosis or telangiectasia grade ≥ 2 between the two arms (log-rank $p=0.923$). There were 2 local and 2 distant recurrences in the daily boost arm. There were 3 local and 1 distant recurrences in the weekly arm, with no difference in 4-year RFS between the two arms (98% in both arms). In addition, extensive QOL assessment between the 2 arms demonstrated comparable results with regard to the patient's experience during and after radiotherapy. In conclusion, the trial demonstrated that a tumor bed boost delivered either daily or weekly is similarly tolerated during accelerated prone breast radiotherapy, with excellent control of disease and comparable cosmetic results (7).

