16.0 Statistical Considerations

This trial is designed to test the feasibility of the combined regimen, defined as limitation of the acute effects to < 10% Grade 3 events.

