16.1 Endpoints

16.1.1 Primary endpoint

The primary endpoint for the study is acute toxicity occurring within 60 days after treatment; the proportion of patients with grade II or III acute skin toxicity.

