16.3 Accrual estimates

Two distinct cohorts will be tested in this study. Based on the algorithm presented in study design (Page 9) some patients will need post-operative radiation to the breast/chest wall alone

(cohort 1) or to the breast and level III /SCV nodes (cohort 2). Since the fields of accelerated radiation are different the 2 cohorts will be accrued separately and analyzed separately.

Estimated number of eligible patients for the trial is 2-4/month. Therefore, we estimate that the required 74 patients (37 per cohort) will be recruited within 24-36 months.

With 37 patients, we can detect a difference of 18% from a baseline rate of 25% (grade II-III acute dermatitis) with a 2-sided $\alpha = 0.05$ and power of 80% using an exact binomial test. If we observe 15 or more events among these 37 patients, the null hypothesis that the rate is 25% will be rejected. Calculations from PASS 2008, NCSS.

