16.6 Statistical Analysis

16.6.1 Primary Endpoint

The primary endpoint is the occurrence of grade II or greater dermatitis within 60 days of the end of the treatment. The proportion of patients who experience this grade II or greater dermatitis will be estimated with exact 95% confidence intervals.

Patient demographic and disease characteristics at registration will be summarized using frequency distributions for qualitative data and summary statistics (means, medians, standard deviations, etc.) and graphical displays (e.g., Boxplots). Treatment data will be summarized similarly. Descriptive analyses will report the primary endpoint in subgroups defined by radiation regimen and other characteristics.

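### The objective is grade 2-3 dermatitis below 25% in each cohort, but the only written boundary (15 or more of 37) tests for a rate above 25%, no result is tied to the objective, and the stated 80% power is not delivered

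*Combined protocol and SAP*

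**What the plan says.** The Protocol Summary gives the primary objective as "Acute Toxicity: Grade 2-3 dermatitis <25% in each cohort", a target with a direction. Section 1.1 is softer: feasibility is to be tested "by evaluating the proportion of patients who experience grade II-III dermatitis within 60 days of the end of treatment", with no threshold.

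Section 16.3 plans 37 patients in each of two cohorts, analysed separately. It names a two-sided exact binomial test at 0.05 against a baseline rate of 25%, with 80% power for an 18-point difference whose direction is not given. It then writes one boundary: "If we observe 15 or more events among these 37 patients, the null hypothesis that the rate is 25% will be rejected".

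Section 16.6.1 plans estimation only: "The proportion of patients who experience this grade II or greater dermatitis will be estimated with exact 95% confidence intervals". Section 16.4, on criteria for future studies, is marked N/A. No section gives a lower boundary or says which result would meet the objective.

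Two neighbouring definitions also differ. Section 16.1.1 defines the endpoint as "the proportion of patients with grade II or III acute skin toxicity", as do the Protocol Summary and Sections 1.1 and 16.3 in substance, whereas Section 16.6.1 counts grade II or greater. The opening of Section 16.0 gives another feasibility criterion, "defined as limitation of the acute effects to < 10% Grade 3 events", with no count or test attached.

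**The concern.** A boundary at 15 of 37 (40.5% observed) can show only that dermatitis is more frequent than 25%. It cannot show the rate below 25% that the objective names. At the end of the trial the team will have a count, a test result and a confidence interval for each cohort, but no written rule that turns them into a statement about the objective.

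The gap matters most in the middle of the range. Counts of 10 to 14 (27.0% to 37.8% observed) lie above the target yet do not reject 25%. Whether such a cohort missed the objective or was inconclusive could be settled after the data are known. The power statement is affected as well, since a reader will take 80% as the chance of reaching the conclusion that the objective asks for.

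**Working it through.** **Inputs.** n = 37 per cohort, null rate 0.25, two-sided alpha 0.05, 18-point difference, 80% power and the boundary of 15 or more are from Section 16.3. The target below 25% is from the Protocol Summary. The exact 95% confidence interval is from Section 16.6.1. X is the number of events and follows a binomial(37, p) distribution. Intervals are Clopper-Pearson: lower limit = Beta(0.025; x, n−x+1) quantile, upper limit = Beta(0.975; x+1, n−x) quantile.

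**1. The plan's boundary.** P(X ≥ 15 | 0.25) = 0.0272 and P(X ≥ 14 | 0.25) = 0.0577. The upper tail at 15 exceeds 0.025, so 15 does not come from an equal-tailed test, which would need 16 or more (0.0117). It does come from a test that controls the total two-sided error: the probability-ordered exact p-value at 15 is 0.0362. The boundary is therefore reproduced as one half of a total-alpha region.

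**2. The plan's power.** An 18-point difference means 43% or 7%.
- Upward: P(X ≥ 15 | 0.43) = 67.8%. Solving P(X ≥ 15 | p) = 0.80 gives p of about 46.1%, a difference of 21 points.
- Downward: P(X ≤ 3 | 0.07) = 74.2%.

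The 80% is not reproduced in either direction. Moving the upper boundary to 14 gives 78.7% at 43%, but its tail of 0.0577 exceeds 0.05. A two-sided one-sample normal approximation at n = 37 gives 69.1% at 43% and 83.3% at 7%, and it is not the exact test that the plan names.

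**3. The lower region that goes with 15.**
- P(X ≤ 3 | 0.25) = 0.0089, and 0.0089 + 0.0272 = 0.0362 (from unrounded tails), within 0.05.
- P(X ≤ 4 | 0.25) = 0.0284, and 0.0284 + 0.0272 = 0.0556, above 0.05.

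The lower region is 3 or fewer.

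**4. What the planned confidence interval says.**

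| Events | Observed | Exact 95% CI | 25% inside? |
|---|---|---|---|
| 3 | 8.1% | 1.7% to 21.9% | no, below |
| 4 | 10.8% | 3.0% to 25.4% | yes |
| 14 | 37.8% | 22.5% to 55.2% | yes |
| 15 | 40.5% | 24.8% to 57.9% | yes |
| 16 | 43.2% | 27.1% to 60.5% | no, above |

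Test and interval agree that 3 is the largest count showing a rate below 25%. They disagree at 15, where Section 16.3 rejects but the interval still contains 25%.

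**5. Why non-rejection does not show a rate below 25%.** P(X ≤ 14 | p) is 97.3% at p = 0.25, 88.7% at 0.30, 70.7% at 0.35 and 46.4% at 0.40. A cohort whose true rate misses the target by 5 or 10 points would usually fail to reject.

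**The case against.** The best defence is that this is a feasibility study which estimates a rate and watches for excess toxicity. Section 16.3 calls 25% a baseline and writes only the excess-toxicity boundary, Section 1.1 speaks of evaluating a proportion, Section 16.6.1 estimates with an interval, and Section 16.4 sets no go/no-go criterion. That reading is reasonable. If it is the intended one, the repair is small, but the Protocol Summary objective must be reworded, because it states a target below 25%.

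Three stronger readings go beyond the documents.
- A reader might infer that 14 or fewer events has no meaning at all. The named test and interval fix the statistical result at every count; what is absent is the link to the objective.
- A reader might infer that the plan would count non-rejection as success, so that 12 of 37 (32.4%) could be declared to meet the target. No section says so. The target can also be read as an observed proportion below 25%, that is 9 or fewer of 37 (24.3%), and on that reading 12 of 37 simply fails. This reading is not written either.
- A reader might infer that the trial must be enlarged. That would rest on background rates from other endpoints, scoring systems and populations, and the smallest sample sizes reaching 80% are peaks of a saw-toothed power curve. Nothing here requires a new sample size.

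The grade 4 ambiguity is minor in practice: the Background reports no grade 4 dermatitis among 90 patients in NYU 03-30, and nothing above grade 2 acute skin toxicity in the nodal trial.

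**Conclusion.** The point holds and should be fixed. The one written decision boundary runs in the opposite direction to the stated objective, and neither the implied lower region (3 or fewer of 37) nor the planned interval is connected to that objective. Non-rejection has probability 89% at a true rate of 30% and 71% at 35%, so it is not evidence of a rate below 25%. The stated 80% power is 67.8% for the written boundary at 43%, and 74.2% for the implied lower region at 7%.

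These results assume exactly 37 analysed patients per cohort, independent binomial outcomes and one consistent event definition. Section 16.2 analyses all registered patients, so the counts shift if a cohort closes above or below 37. The documents do not settle whether a claim of a rate below 25% or a screen for excess toxicity was intended; that choice belongs to the sponsor.

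**What to change.** In the Protocol Summary objective, Section 16.3 and Section 16.6.1, state one reading for each cohort.

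(i) **A claim that the rate is below 25%.** It is met only if the upper limit of the planned exact 95% confidence interval is below 25%, which is 3 or fewer of 37. By that interval, 4 to 15 events is inconclusive and 16 or more shows a rate above 25%. If 15 is to stay as the upper boundary, name the total-alpha exact test (size 0.036) as the decision rule and note that the interval at 15 still contains 25%.

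(ii) **A screen for excess toxicity.** Fifteen or more events signals a rate above 25%. Reword the Protocol Summary objective to estimating the rate, and say that 14 or fewer does not show a rate below 25%.

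If an observed proportion below 25% (9 or fewer of 37) was meant, say so and call it descriptive.

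Under any choice, replace the 80% with the exact power of the chosen rule: 74.2% at 7% for 3 or fewer; for the upper boundary at 43%, 67.8% with 15 or more, or 55.1% with 16 or more. Use one endpoint definition throughout, stating whether grade 4 counts, and reconcile it with the Grade 3 feasibility definition in Section 16.0.

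The cost is wording only, with n unchanged. Under (i) the sponsor accepts a power of 74.2% at 7%.

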16.4 Criteria for future studies

N/A

16.5 Interim analyses

None planned

16.6 Statistical Analysis

16.6.1 Primary Endpoint

The primary endpoint is the occurrence of grade II or greater dermatitis within 60 days of the end of the treatment. The proportion of patients who experience this grade II or greater dermatitis will be estimated with exact 95% confidence intervals.

Patient demographic and disease characteristics at registration will be summarized using frequency distributions for qualitative data and summary statistics (means, medians, standard deviations, etc.) and graphical displays (e.g., Boxplots). Treatment data will be summarized similarly. Descriptive analyses will report the primary endpoint in subgroups defined by radiation regimen and other characteristics.

16.6.2 Secondary Endpoints

See primary endpoint.

16.6.3 Exploratory Endpoints

Local recurrence rates will be reported along with 95% confidence intervals. Kaplan Meier curves will be used to estimate recurrence free and overall survival.

Appendix 1. – Common Toxicity Criteria

Acute Toxicity from *Common Terminology Criteria for Adverse Events v4.0 (CTCAE)*, Published: May 28, 2009

	Grade 0	Grade 1	Grade 2	Grade 3	Grade 4
FATIGUE	No change	Mild fatigue over baseline	Moderate or causing difficulty performing some ADL	Severe fatigue interfering with ADL	Disabling
RADIATION DERMATITIS	No change	Faint erythema or dry desquamation	Moderate to brisk erythema; patchy moist desquamation, mostly confined to skin folds and creases; moderate edema	Moist desquamation other than skin folds and creases; bleeding induced by minor trauma or abrasion	Skin necrosis or ulceration of full thickness dermis; spontaneous bleeding from involved site
PAIN	No pain	Mild pain not interfering with function	Moderate pain; pain or analgesics interfering with function, but not interfering with ADL	Severe pain; pain or analgesics severely interfering with ADL	Disabling

Table 1. RTOG/EORTC and LENT/SOMA classification of late effects

RTOG/EORTC	Grade 1	Grade 2	Grade 3	Grade 4
Skin	Slight atrophy, pigmentation change, some hair loss	Patchy atrophy, moderate telangiectasia, total hair loss	Marked atrophy, gross telangiectasia	Ulceration
Subcutaneous tissue	Slight induration (fibrosis), and loss of subcutaneous fat	Moderate fibrosis, but asymptomatic; slight field contracture, $\leq 10\%$ linear reduction	Severe induration and loss of subcutaneous tissue, field contracture, $\geq 10\%$ linear reduction	Necrosis
LENT/SOMA				
Breast				
Subjective				
Pain	Occasional and minimal Hypersensation, pruritus	Intermittent and tolerable	Persistent and intense	Refractory and excruciating
Objective				
Telangiectasia	$<1\text{ cm}^2$	$1\text{--}4\text{ cm}^2$	$>4\text{ cm}^2$	
Fibrosis	Barely palpable, increased density	Definite increased intensity and firmness	Very marked density, retraction, and fixation	
Edema	Asymptomatic	Symptomatic	Secondary dysfunction	
Retraction, atrophy	10–25%	$>25\text{--}40\%$	$>40\text{--}75\%$	Whole breast
Ulcer	Epidermal only, $<1\text{ cm}^2$	Dermal only, $>1\text{ cm}^2$	Subcutaneous	Bone exposed, necrosis
Lymphedema, arm circumference	2–4-cm increase	$>4\text{--}6\text{-cm}$ increase	$>6\text{-cm}$ increase	Useless arm
Skin				
Pigmentation change	Transitory, slight	Permanent, marked	—	—

Abbreviations: RTOG = Radiation Therapy Oncology Group; EORTC = European Organization for Research and Treatment of Cancer; LENT = Late Effects Normal Tissue Task Force; SOMA = subjective, objective, management, and analytic.

Appendix 2 - Toxicity Tracking Form

PHYSICIAN'S PROGRESS NOTE

Fraction: 1-5 6-10 11-15 1 mo F/U 3 mo F/U

The following critical elements of the patient's weekly exam have been covered:

- Chart & Dosimetry, Treatment set up & positioning review*
- Port Film or image review*
- Examination of patient for evaluation and progress of treatment (see notes below)*

Progress note: _____

Please indicate Toxicity due to Radiation Treatment on the following chart:

	Grade 0	Grade 1	Grade 2	Grade 3	Grade 4
FATIGUE					
	No change	Mild fatigue over baseline	Moderate or causing difficulty performing some ADL	Severe fatigue interfering with ADL	Disabling
RADIATION DERMATITIS					
	No change	Faint erythema or dry desquamation	Moderate to brisk erythema; patchy moist desquamation, mostly confined to skin folds and creases; moderate edema	Moist desquamation other than skin folds and creases; bleeding induced by minor trauma or abrasion	Skin necrosis or ulceration of full thickness dermis; spontaneous bleeding from involved site
PAIN (Breast)					
	No pain	Mild pain not interfering with function	Moderate pain; pain or analgesics interfering with function, but not interfering with ADL	Severe pain; pain or analgesics severely interfering with ADL	Disabling

Attending Signature: _____ Date: _____

Appendix 3 – Quality Of Life Questionnaires

Appendix 3.1 Quality of Life questionnaire used at baseline

Form QLB (01-25-2005)

Quality of Life Questionnaire - Baseline

Page 1 of 7

Patient Initials ,
Last First Middle

Patient Study ID

Participants should complete this questionnaire at baseline (after consent and prior to randomization). The first page is to be completed by a clinical staff member. Fill in the items listed on this page, print the patient's study ID at the top of pages 2 through 7 and give the questionnaire to the patient for completion. After the patient has completed the questionnaire, verify that the date has been recorded at the top of page 2.

Please administer the questionnaire at an office visit if possible. If that is not possible, mail the questionnaire to the patient, then call to ask for the patient's responses over the phone. If all efforts to administer the scheduled questionnaire fail, a B-39 QMD form should be submitted instead.

Mark Circles Like This: → ●

Institution Name / Affiliate Name

Staff Member Administering Form

Last Name

First Name

Phone

Are data amended? Yes (If yes, circle the amended items.)

Time point for this questionnaire (Do not mark in this box.)

● Baseline (after consent, before randomization)

Last week of radiation therapy
45-60 days after starting radiotherapy
Two years after adjuvant radiation therapy

This form is being filled out: (Mark one.)

By participant in doctor's office By clinical staff, on phone with participant
 By participant not in doctor's office Other

Record the participant's study ID on each of the remaining pages before giving the questionnaire to the participant.

Patient
Study ID Date this questionnaire is completed:
Month Day Year*(For example, if you were completing the questionnaire on September 8, 2004, you would write 09 08 2004 in the boxes.)*

Thank you for completing this questionnaire.

We are interested in your evaluation of your physical appearance and functioning since you have been treated for breast cancer. Please rate the following items on this four-point scale, according to your evaluation at this point in time.

	Difference between treated and untreated breast and area			
	None	Slight	Moderate	Large
1 Breast size	1	2	3	4
2 Breast texture (hardening)	1	2	3	4
3 Arm heaviness	1	2	3	4
4 Nipple appearance	1	2	3	4
5 Shoulder movement	1	2	3	4
6 Arm movement	1	2	3	4
7 Breast pain	1	2	3	4
8 Ability to lift objects	1	2	3	4
9 Fit of shirt sleeve	1	2	3	4
10 Breast tenderness	1	2	3	4
11 Shoulder stiffness	1	2	3	4
12 Breast shape	1	2	3	4
13 Breast elevation (how high the breast is)	1	2	3	4
14 Scar tissue	1	2	3	4
15 Shoulder pain	1	2	3	4
16 Arm pain	1	2	3	4
17 Arm swelling	1	2	3	4
18 Breast swelling	1	2	3	4
19 Arm stiffness	1	2	3	4
20 Fit of bra	1	2	3	4
21 Breast sensitivity	1	2	3	4
22 Fit of clothing	1	2	3	4

Patient
Study ID

--	--	--	--	--	--	--	--	--

We are interested in your personal reactions to the surgery you have received for your breast cancer. Please answer the following questions by circling one (1) number. Please note that the response options are labeled at the end-points only. However, you can and should use all of the points on the scale as appropriate to best convey your response.

1. To what extent has your surgery **disrupted** your normal daily activities?

0	1	2	3	4	5	6	7	8	9	10
---	---	---	---	---	---	---	---	---	---	----

Not at all A lot

2. To what extent has your surgery **disrupted** your normal recreational activities?

0	1	2	3	4	5	6	7	8	9	10
---	---	---	---	---	---	---	---	---	---	----

Not at all A lot

3. To what extent has your surgery **disrupted** your normal activities with your family and friends?

0	1	2	3	4	5	6	7	8	9	10
---	---	---	---	---	---	---	---	---	---	----

Not at all A lot

4. To what extent has your surgery **disrupted** your normal sleep pattern?

0	1	2	3	4	5	6	7	8	9	10
---	---	---	---	---	---	---	---	---	---	----

Not at all A lot

5. To what extent has your surgery **reduced** your enjoyment of life?

0	1	2	3	4	5	6	7	8	9	10
---	---	---	---	---	---	---	---	---	---	----

Not at all A lot

6. To what extent has your surgery **disrupted** your regular activities at work (e.g., need to take time off, not getting done as much as you'd like)? If you do not work outside the home for pay, please check this box and go to the next question.

0	1	2	3	4	5	6	7	8	9	10
---	---	---	---	---	---	---	---	---	---	----

Not at all A lot

7. How **satisfied** are you with the length of time your treatment has taken to this point in time?

0	1	2	3	4	5	6	7	8	9	10
---	---	---	---	---	---	---	---	---	---	----

Not at all A lot

8. How **disruptive** has your surgery been to the other important people in your life (e.g., family and close friends)?

0	1	2	3	4	5	6	7	8	9	10
---	---	---	---	---	---	---	---	---	---	----

Not at all A lot

Patient Study ID

These questions are about how you feel and how things have been with you during the past 4 weeks. For each question, please give the one answer that comes closest to the way you have been feeling.

How much of the time during the past 4 weeks...

	All of the time	Most of the time	Some of the time	A little of the time	None of the time
1. Did you feel full of life?	1	2	3	4	5
2. Did you have a lot of energy?	1	2	3	4	5
3. Did you feel worn out?	1	2	3	4	5
4. Did you feel tired?	1	2	3	4	5

5. Rate your pain at its worst in the past four weeks. (Circle one number.)

0	1	2	3	4	5	6	7	8	9	10
---	---	---	---	---	---	---	---	---	---	----

No pain

Pain as bad as you can imagine

6. Rate your pain at its least in the past four weeks. (Circle one number.)

0	1	2	3	4	5	6	7	8	9	10
---	---	---	---	---	---	---	---	---	---	----

No pain

Pain as bad as you can imagine

7. Rate your pain on average in the past four weeks. (Circle one number.)

0	1	2	3	4	5	6	7	8	9	10
---	---	---	---	---	---	---	---	---	---	----

No pain

Pain as bad as you can imagine

8. Rate how much pain you have right now. (Circle one number.)

0	1	2	3	4	5	6	7	8	9	10
---	---	---	---	---	---	---	---	---	---	----

No pain

Pain as bad as you can imagine

9. Are you currently receiving treatments or taking medications for your pain?

Circle one: Yes No

Patient
Study ID

By circling one (1) number per line, please indicate how much you have been bothered by each of the following problems in the past four weeks.

	Not bothered at all	A little bothered	Some- what bothered	Bothered quite a bit	Bothered very much
Fever or shivering (shaking, chills)	0	1	2	3	4
Swelling of breast (breast feels larger)	0	1	2	3	4
Breast heaviness	0	1	2	3	4
Breast warm to touch	0	1	2	3	4
Breast skin is red	0	1	2	3	4
Breast skin is tanned	0	1	2	3	4
Breast skin or area around nipple is pale in color	0	1	2	3	4
Breast skin is flaking or peeling	0	1	2	3	4
Bleeding or fluid leakage from breast	0	1	2	3	4
Breast itching	0	1	2	3	4
Blisters on the breast (or breast skin moist and raw)	0	1	2	3	4
Coughing	0	1	2	3	4
Difficulty breathing	0	1	2	3	4
Muscle aches	0	1	2	3	4
Rib or chest wall pain	0	1	2	3	4
Infections	0	1	2	3	4
Slow healing of breast wounds	0	1	2	3	4
Visible small blood vessels (spider veins)	0	1	2	3	4
Pockmarks or puncture wounds on breast	0	1	2	3	4
Thickening of breast skin	0	1	2	3	4
Hardening of breast	0	1	2	3	4
Breast or nipple numbness	0	1	2	3	4
Sharp shooting pains or twinges in the breast	0	1	2	3	4

Patient
Study ID

By circling one (1) number per line, please indicate how much you have been bothered by each of the following problems in the past four weeks.

	Not bothered at all	A little bothered	Some- what bothered	Bothered quite a bit	Bothered very much
Breast aches	0	1	2	3	4
Breast tenderness	0	1	2	3	4
Decrease or lack of arousal on breast	0	1	2	3	4
Any other problems? (Specify below)	0	1	2	3	4

Specify other problems:

You have been treated with breast conserving therapy for breast cancer. As you know, a reason for choosing this treatment is to keep a breast that looks and feels as close to normal as possible. Your opinion concerning the appearance of your breast is valuable to us. Circle the number next to the word that best describes how your breast looks now.

1	EXCELLENT: when compared to the untreated breast or the original appearance of the breast, there is minimal or no difference in the size or shape of the treated breast. The way the breast feels (its texture) is the same or slightly different. There may be thickening, scar tissue or fluid accumulation within the breast, but not enough to change the appearance.
2	GOOD: there is a slight difference in the size or shape of the treated breast as compared to the opposite breast or the original appearance of the treated breast. There may be some mild reddening or darkening of the breast. The thickening or scar tissue within the breast causes only a mild change in the shape or size.
3	FAIR: obvious differences in the size and shape of the treated breast. This change involves a quarter or less of the breast. There can be moderate thickening or scar tissue of the skin and the breast, and there may be obvious color changes.
4	POOR: marked change in the appearance of the treated breast involving more than a quarter of the breast tissue. The skin changes may be obvious and detract from the appearance of the breast. Severe scarring and thickening of the breast, which clearly alters the appearance of the breast, may be found.

My satisfaction about the treatment and results is: (Select the phrase that best describes your satisfaction.)

Totally
satisfied

Somewhat
satisfied

Neither
satisfied nor
dissatisfied

Somewhat
dissatisfied

Totally
dissatisfied

Patient
Study ID

Before any treatment to your breast, the size of your breasts was: (Select the phrase that best describes your breast size prior to treatment.)

Larger
on left

The same on
both sides

Larger
on right

The size of your breasts now is: (Select the phrase that best describes your breast size now.)

Larger
on left

The same on
both sides

Larger
on right

Thank you for completing this questionnaire!

